14.3.12.4	SAEs by SOC, PT and relationship - Period [3rd dose; 4th dose[X			
14.3.12.5	SAEs by SOC, PT and relationship - Period [4th dose; 5th dose[X			
14.3.12.6	SAEs by SOC, PT and relationship - Period [5th dose; Week 36]		X			
14.3.12.7	SAEs by SOC, PT and relationship - Period [Last dose; Week 36/Early Termination]		X			
14.3.13.1	SAEs by SOC, PT and intensity - Before 1st dose		X			
14.3.13.2	SAEs by SOC, PT and intensity - Period [1st dose; 2nd dose[X			
14.3.13.3	SAEs by SOC, PT and intensity - Period [2nd dose; 3rd dose[X			
14.3.13.4	SAEs by SOC, PT and intensity - Period [3rd dose; 4th dose[X			
14.3.13.5	SAEs by SOC, PT and intensity - Period [4th dose; 5th dose[X			
14.3.13.6	SAEs by SOC, PT and intensity - Period [5th dose; Week 36]		X			
14.3.13.7	SAEs by SOC, PT and intensity - Period [Last dose; Week 36/Early Termination]		X			
14.3.14	SAEs leading to permanent study drug discontinuation by SOC and PT		X			
14.3.15.1	Hematology - Value at each visit		X			
14.3.15.2	Hematology - Change from baseline		X			
14.3.15.3	Hematology - Abnormalities at each visit		X			
14.3.15.4	Hematology - Grade at each visit		X			
14.3.16.1	Chemistry - Value at each visit		X			
14.3.16.2	Chemistry - Change from baseline		X			
14.3.16.3	Chemistry - Abnormalities at each visit		X			
14.3.16.4	Chemistry - Grade at each visit		X			
14.3.17.1	Coagulation - Value at each visit		X			
14.3.17.2	Coagulation - Change from baseline		X			
14.3.17.3	Coagulation - Abnormalities at each visit		X			

Statistical Analysis Plan

Study Name: IFN-K-002

SAP version & date: v4, 18/Jun/2018

Number	Title	Screened	SAF	FAS	PP	Other
14.3.17.4	Coagulation - Grade at each visit		X			
14.3.18	Urinalysis - Value at each visit		X			
14.3.19	Incidence of severe infections at D0		X			
14.3.20.1	Weight and BMI - Value at each visit		X			
14.3.20.2	Weight and BMI - Change from baseline		X			
14.3.21	Physical examination, Body system at each visit		X			
14.3.22.1	Vital signs - Value at each visit		X			
14.3.22.2	Vital signs - Change from baseline		X			
14.3.23	ECG - Abnormalities at each visit		X			
14.3.24	Concomitant medications		X			

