12.1.2 Intensity of event

All AEs shall be graded by the Investigator using the World Health Organization (WHO) Toxicity Scale (Appendix 10). If an event cannot be graded by the WHO scale, the Investigator shall evaluate the severity according to a similar 4-point scale using the following definitions:

- **Mild:** The subject is aware of the event or symptom, but the event or symptom is easily tolerated.
- **Moderate:** The subject experiences sufficient discomfort to interfere with or reduce his or her usual level of activity.
- **Severe:** Significant impairment of functioning: the subject is unable to carry out usual activities.
- **Life threatening:** any AE that places the patient, in the view of the Investigator, at immediate risk of death from the event as it occurred, i.e., it does not include an event that had occurred in a more severe form, might have caused death.

Changes in the severity of an AE should be documented to allow an assessment of the duration of the event at each level of intensity to be performed. AEs characterized as intermittent require documentation of onset and duration of each episode.

The following **local AEs** at the injection site (pain, redness, swelling, itching and induration) will be graded by study center staff and by the patient on the diary cards according to the intensity scale in Table 7.

Table 7 Intensity Scale for Local Reactions

Local Reaction	Mild (Grade 1)	Moderate (Grade 2)	Severe (Grade 3)
Pain	Does not interfere with activity	Interferes with activity	Prevents daily activity
Redness*	> 0 to < 30 mm	≥ 30 to < 120 mm	≥ 120 mm
Swelling*	> 0 to < 30 mm	≥ 30 to < 120 mm	≥ 120 mm
Itching	Does not interfere with activity	Interferes with activity	Prevents daily activity
Induration	> 0 to < 30 mm	≥ 30 to < 120 mm	≥ 120 mm

*Measure at greatest single diameter

The following **systemic reactions** (fever, headache, fatigue, myalgia and nausea) will be graded by study site staff and by the patient on the diary cards according to the intensity scale in Table 8.

Table 8 Intensity Scale for Systemic Reactions

Systemic Reaction	Mild (Grade 1)	Moderate (Grade 2)	Severe (Grade 3)
Fever (°C)*	37.1 - 38.0	38.1 - 40.0	> 40.0
Headache	Mild	Moderate or severe but transient	Unrelenting and severe
Fatigue	Increased fatigue over baseline, but not altering normal activities	Moderate or causing difficulty performing some activities	Severe or loss of ability to perform some activities

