13.9.5 Analysis of the Safety Endpoints

Safety data will be presented and analyzed using the SP:

- SAEs will be listed and summarized in a table, including a description and severity and duration of each event
- All AEs (including SAEs) will be listed, and their frequency, severity, and duration will be summarized for each treatment arm. Additionally, summary statistics per the number of doses administered will be obtained
- Premature withdrawals from the study will be displayed and summarized by primary reason
- Abnormal physical examination findings will be summarized over time
- Concomitant medications will be presented in summary tables and listings
- An association between the antibody response and the severity and/or frequency and/or duration of symptoms associated with kinoid administration will be investigated.
- The incidence of severe infections based on the total T-lymphocyte count (lymphocytes < 1000 versus lymphocytes > 1000/mm³) at the visit 2 (D0) will be analyzed.

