5.2.5.2 Adverse events

Adverse event tabulations:

Tabulation of adverse events will present for each cell the following information: number of patients with at least one occurrence of the event, corresponding percentage and number of events (if relevant).

The following tables will be produced for the Safety population as well as by treatment group:

The definition of TEAEs is described in section 4.2.1.

The following period will be defined:

- before first dose
- [1st dose; 2nd dose[
- [2nd dose; 3rd dose[
- [3rd dose; 4th dose[
- [4th dose; 5th dose[
- [5th dose; Week 36]
- [Last dose; Week 36/Early Termination] (for AE which cannot be classified in the previous periods due to dose not received or premature study termination)

Summary table of adverse events (Statistical Table 14.3.2):

- Any AE
- Any TEAE
- Any TEAE by period
- Any TEAE leading to study treatment temporarily discontinuation
- Any TEAE leading to study treatment permanent discontinuation
- Any TEAE of intensity severe or more
- Any TEAE considered related to the study treatment (possibly or probably related)
- Any SAE
- Any SAE by period
- Any Treatment Emergent SAE (TESAE)
- Any TESAE leading to study treatment temporarily discontinuation
- Any TESAE leading to study treatment permanent discontinuation
- Any TESAE considered related to the study treatment (possibly or probably related)
- Any TESAE of intensity severe or more

Statistical Analysis Plan

Study Name: IFN-K-002

SAP version & date: v4, 18/Jun/2018

- Death

Detailed Tables:

All tables listed below will be presented by period (except if otherwise specified):

- Solicited local reactions during a 7-day follow-up period after each study product administration by SOC and PT (Statistical Tables 14.3.3.1 to 14.3.3.6)
- Solicited local reactions during a 7-day follow-up period after each study product administration by SOC, PT and intensity (Statistical Tables 14.3.4.1 to 14.3.4.6)
- Solicited systemic reactions during a 7-day follow-up period after each study product administration by SOC and PT (Statistical Tables 14.3.5.1 to 14.3.5.6)
- Solicited systemic reactions during a 7-day follow-up period after each study product administration by SOC, PT and intensity (Statistical Tables 14.3.6.1 to 14.3.6.6)
- TEAEs by SOC and PT (Statistical Tables 14.3.7.1 to 14.3.7.6)

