- TEAEs by SOC, PT and status of IFN α neutralizing antibodies (positive/negative) at time of event (only on patients IFN-K treated) (Statistical Tables 14.3.7.7 to 14.3.7.10)
- TEAEs by SOC, PT and relationship (Statistical Tables 14.3.8.1 to 14.3.8.6)
- TEAEs by SOC, PT and intensity (Statistical Tables 14.3.9.1 to 14.3.9.6)
- TEAEs leading to permanent study treatment discontinuation by SOC and PT (Statistical Table 14.3.10) (only throughout the study)
- SAEs by SOC and PT (Statistical Tables 14.3.11.1 to 14.3.11.7)
- SAEs by SOC, PT and status of IFN α neutralizing antibodies (positive/negative) at time of event (only on patients IFN-K treated) (Statistical Tables 14.3.11.8 to 14.3.11.11)
- SAEs by SOC, PT and relationship (Statistical Tables 14.3.12.1 to 14.3.12.7)
- SAEs by SOC, PT and intensity (Statistical Tables 14.3.13.1 to 14.3.13.7)
- SAEs leading to permanent study treatment discontinuation by SOC and PT (Statistical Table 14.3.14)

The following rules will be applied to analyze the occurrence of AE according to the status of IFN α neutralizing antibodies (positive/negative):

- For adverse event which occurred between dose 1 and dose 3 included, status of neutralizing capacity will not be assessed
- For adverse event which occurred between 3rd dose (excluded) and Visit 6 (included), status of neutralizing capacity at visit 6 will be used
- For adverse event which occurred between Visit 6 (excluded) and Visit 9 (included), status of neutralizing capacity at visit 9 will be used
- For adverse event which occurred between Visit 9 (excluded) and Visit 12 (included), status of neutralizing capacity at visit 12 will be used

Statistical Analysis Plan

Study Name: IFN-K-002

SAP version & date: v4, 18/Jun/2018

Statistical Analysis Plan

Study Name: IFN-K-002

SAP version & date: v4, 18/Jun/2018

Adverse events listings:

All adverse events (including solicited local and systemic reactions) recorded during the study will be presented in Listings. The following information (if available) will be included in the listings (non-exhaustive list):

- Patient identifier
- Age, Ethnic origin (see section 9 Derived data), gender, weight
- The adverse event (System organ class, preferred term, reported term)
- Start date, end date, duration, period
- Severity (e.g., mild, moderate, severe)
- Seriousness (serious/non-serious)
- Action taken
- Outcome
- Relatedness assessment

Listings will be provided for:

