7.3 Adverse events

Analysis of solicited local & systemic reactions 1-hour post study product administration was planned in the protocol. Time of these AEs was not recorded into the eCRF. This analysis will not be done.

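### The by-arm summary of adverse event duration planned in protocol 13.9.5 has no table in the SAP, and SAP section 7 does not declare the omission

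*SAP*

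**What the plan says.** **Protocol.** Section 13.9.5 states: "All AEs (including SAEs) will be listed, and their frequency, severity, and duration will be summarized for each treatment arm". Listing and by-arm summary are separate commitments in that sentence, and duration stands beside frequency and severity without qualification. The same section says of serious events: "SAEs will be listed and summarized in a table, including a description and severity and duration of each event". It also says: "An association between the antibody response and the severity and/or frequency and/or duration of symptoms associated with kinoid administration will be investigated". Section 12.1.2 has sites document changes in severity "to allow an assessment of the duration of the event at each level of intensity to be performed".

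**SAP.** Section 5.2.5.2 sets the content of every adverse event table cell: "number of patients with at least one occurrence of the event, corresponding percentage and number of events (if relevant". The tables are produced for the safety population and by treatment group. They are split by system organ class and preferred term, and then variously by intensity, relationship, neutralizing antibody status, treatment discontinuation and dose period. A typical title in section 10.1 is "SAEs by SOC, PT and intensity - Period [5th dose; Week 36". Section 9 derives Event Duration as end date minus start date plus one. Section 5.2.5.2 names it, where available, among the listing items: "Start date, end date, duration, period".

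**Declared changes.** SAP 7.3, on adverse events, records one change: "Analysis of solicited local & systemic reactions 1-hour post study product administration was planned in the protocol", and that analysis is withdrawn because the event times were not captured. It does not mention duration.

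**The concern.** Both arms receive the same ISA 51 VG emulsion, so the adjuvant alone may produce local reactions in both. If so, the antigen's added contribution need not show in how many patients react. It could show in how severe the reactions are, which the SAP compares, or in how long they last, which it does not summarise. Duration is therefore a separate aspect of tolerability, and the protocol planned to report it by arm.

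Traceability is also at stake. Protocol section 13 says that major departures from its statistical plan, and the reasons for them, will be described in the SAP. A planned safety summary that disappears without comment leaves the reader unable to tell a decision from an oversight.

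**Working it through.** No power or sample size arithmetic applies. The check sets the protocol's commitment against the SAP's outputs.

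**1. Each element of the by-arm commitment**

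| Element (protocol 13.9.5) | By-arm SAP table | Patient listing |
|---|---|---|
| Frequency | Yes: 14.3.2 onwards | Yes |
| Severity | Yes: 14.3.4 (solicited local), 14.3.6 (solicited systemic), 14.3.9 (TEAEs), 14.3.13 (SAEs) | Yes |
| Duration | None | Yes: 16.2.7.1 to 16.2.7.4, where available |

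**2. Count of table groups.** Groups 14.3.2 to 14.3.14 number 14 − 2 + 1 = 13. Groups with intensity in the title: 4. Groups with event duration in the title: 0. The cell rule in SAP 5.2.5.2 does not bring duration in under another title, because it allows only patients, percentage and number of events.

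**3. Other places where duration might be covered.** SAP 5.2.5.1 and Table 14.3.1 contain a duration, but it is the time from first to last administration, which is exposure. SAP section 9 defines Event Duration but assigns it to no table.

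**4. Declared changes.** SAP 7.1 to 7.5 cover the renaming of the ITT population, the added mixed model, the added composite SRI-4, the removed change-in-therapy analysis, the removed one-hour analysis, the replacement of percent change by change for laboratory data, and the added LLDAS. Several of these are small. Event duration is not among them. The part of the SAP change history that could be read is also silent; its version 4 entry was not in the text available for this check.

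**5. What the listings ask of a reader.** With 178 planned patients and up to five administrations each, there are at most 178 × 5 = 890 seven-day diaries. Comparing durations between arms from line listings on that scale is not a summary by arm.

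**6. Limits of the existing variable.** The diary runs from Day 1 to Day 7, so a reaction present throughout has a diary duration of at most 7 − 1 + 1 = 7 days, whenever it really ended. An event still ongoing has no end date, so the formula returns nothing. The date rules in SAP 5.3.2 deal with missing or partial onset dates and do not supply an end date. Any duration table must therefore show truncated and ongoing events separately.

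**The case against.** The strongest reply is that this is a documentation gap of little weight. Protocol 13.4 and SAP 4.2.1 define the safety endpoints through occurrence, intensity and relationship, and neither names duration. Protocol 13.9 calls itself a brief description and leaves full details to the SAP, and only major departures must be described there. The protocol also reports that the earlier study of this product saw few local or systemic reactions, transient and mild to moderate, so there may be little duration to compare. All of this stands, and it is why the point is minor. It does not remove the point: the sentence in 13.9.5 is specific, and SAP section 7 records changes no larger than this one.

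A reader might infer more than the documents support, in four ways.

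- *That the SAP compares only whether events occurred.* It does not stop there: intensity is tabulated by arm and by dose period for solicited local reactions, solicited systemic reactions, TEAEs and SAEs.
- *That duration goes unreported.* It is derived and is named as a listing column. Only the by-arm summary is missing.
- *That the separate SAE commitment is broken.* That sentence asks for the description, severity and duration of each event, and Listing 16.2.7.4 largely provides this line by line.
- *That the antibody association is broken.* The protocol joins severity, frequency and duration there with and/or. SAP Tables 14.3.7.7 to 14.3.7.10 and 14.3.11.8 to 14.3.11.11 give event frequency by antibody status in IFN-K patients, which meets that wording.

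**Conclusion.** The point holds in a narrow form. The protocol commits to a by-arm summary of adverse event duration, no SAP table provides one, and SAP section 7 does not declare its removal. The consequence is that a difference between arms in how long reactions last would be visible only in patient listings.

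Severity is minor. Neither co-primary endpoint is touched, frequency and intensity are still compared by arm, and the duration data are kept. How much would actually be missed cannot be sized from the documents: they give no expected reaction rate or duration for this trial, and the planned safety tables are descriptive with no arm tests, so a power figure would rest wholly on assumed inputs. The conclusion assumes only that the table titles in SAP 10.1 and the cell rule in 5.2.5.2 describe the tables as they will be produced.

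**What to change.** Add to SAP 5.2.5.2 and 10.1 descriptive duration summaries by treatment arm, using the Event Duration variable already in section 9. Give n, median, Q1 to Q3, range and number ongoing for:

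- solicited local reactions;
- solicited systemic reactions;
- TEAEs;
- SAEs.

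State how incomplete durations are shown. For solicited reactions, report the number still present on diary Day 7 as truncated. Censoring at Week 36 would not suit data collected on a seven-day card. For other events, report the number ongoing at Week 36 or at early termination.

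If the sponsor means to drop the summary, declare this in SAP 7.3 with the reason. Either course resolves the discrepancy.

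The cost is a few extra descriptive tables, or one declared and justified entry in SAP 7.3. No new data collection is needed, since start and end dates and duration are already listing items.

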10.2 List of figures

Number	Title	Screened	SAF	FAS	PP	Other
14.2.1	Sensitivity efficacy analysis - First co-primary endpoint - MMRM - Model diagnostic			X		
14.2.2	Immunogenicity analysis - Anti-IFN α binding antibody titers - Reverse cumulative distribution curves				X	
14.2.3	Immunogenicity analysis - NC50 - Reverse cumulative distribution curves				X	
14.2.4	Immunogenicity analysis - Anti-KLH binding antibody titers - Reverse cumulative distribution curves				X	

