5.4.3 Clinical Experience

In a Phase I-II, randomized, double-blind, placebo-controlled dose escalation study, IFN-K has been evaluated in patients with mild to moderate SLE (EudraCT# 2009-012059-47, CT.gov# NCT01058343, Lauwers *et al.*, 2013). Twenty-eight patients were enrolled and distributed among 4 parallel groups receiving 30, 60, 120 or 240 µg IFN-K or placebo at days 0, 7 and 28 with a conditional fourth injection at month 3 for 50% of the patients in the 60, 120, and 240 µg dose groups. A total of 21 patients were exposed to IFN-K, and 7 patients received the placebo.

For the patients receiving IFN-K, major conclusions on biologic effect were:

- An immunogenic effect of IFN-K is observed after 3 immunizations irrespective of the dose. Neutralization of the IFN gene signature is already visible 10 days after completion of the 3-dose course, and it peaks at 8 weeks post-dose 3.
- All patients developed an antibody response against IFN α , and antibody levels were significantly higher in patients with a positive IFN gene signature than in patients with a negative signature. Also, IFN α -mediated and SLE-associated gene expression was reduced more in patients immunized with IFN-K than in patients treated with the placebo. This decrease in the expression of SLE-associated genes significantly correlated with anti-IFN α antibody levels and was more pronounced in patients with the highest IFN gene signature before immunization. Furthermore, the increase in C3 complement from baseline significantly correlated with the anti-IFN α antibody level.
- Two patients in the phase I-II study were taking prednisone at 15 and 20 mg/day, with no indication of a decreased anti-IFN α antibody response.
- Patients with a positive IFN gene signature at baseline developed higher antibody titers and a more pronounced neutralization of the IFN gene signature, together with an impact on disease

biomarkers than patients with a negative IFN gene signature. IFN α -neutralizing activity was detected in 3 out of 6 subjects treated with 60 μ g IFN-K, in 3 out of 6 subjects treated with 120 μ g IFN-K, and in 4 out of 5 subjects treated with 240 μ g IFN-K, but was not detected in subjects treated with 30 μ g IFN-K or with placebo or at baseline in any subjects.

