5.6 Benefit-Risk Assessment

The down-regulation of IFN α has been suggested to be possibly beneficial in patients suffering from SLE (Yao *et al.*, 2009b). IFN-K acting as active immunization against IFN α has the capability to induce anti-IFN α antibodies to neutralize IFN α biological activity and therefore has the potential to treat the deleterious effects consequent to over-expression of the cytokine IFN α observed in patients with SLE.

Preclinical data in lupus mice injected with IFN-K, have shown that treatment with IFN-K elicit production of anti-IFN neutralizing antibodies, and significantly reduced progression of the disease, as demonstrated by an increased survival rate, and a reduction in proteinuria. In long term treatment administration in mice models and in repeat toxicity studies in monkeys, IFN-K was well tolerated at the dose, and with the route and the schedule of administration equivalent to the ones proposed in the planned clinical trial (see current version of the IB).

Over the 28 patients enrolled in the previous Phase I-II clinical study, 21 patients with SLE were administered with IFN-K as an intramuscular injection (Lauwerys *et al.*, 2013). IFN-K was generally well tolerated. Few local (including tenderness, swelling, erythema and itching) or systemic reactions were reported, and were mild to moderate in severity and transient in nature. Eight serious adverse events (SAEs) were reported in 5 patients across the whole study (main and extended Follow-up). Two of the SAEs were SUSARs (one flare of underlying lupus occurred for a patient who had received only one injection of IFN-K at 240 μ g and one colon cancer with liver metastasis in a patient who received 4 injections of IFN-K at 120 μ g) (for further details see the current version of the IB).

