13.9.6 Analysis of the Exploratory Endpoints

- Clinical response by assessing disease activity using: 28-Tender and Swollen Joint Counts and Joint Pain VAS will be analyzed using a t-test
- Number of SLE flares will be analyzed using frequency table methods
- Time to first SLE flare in patients will be analyzed using life-table methods
- Proportion of patients with an increase or addition in lupus therapy will be analyzed using frequency table methods

- Proportion of treatment failure will be analyzed using frequency table methods. Patients will be considered as treatment failure if they receive more than 5 mg prednisone equivalent/day at any time between Week 24 (Visit 9) and Week 36 (Visit 12) or if their CS dose is increased above the Week 24 level or if any increase of immunosuppressive treatment between Week 12 and Week 36 above CS dose at Week 12 is recorded.
- Changes in the SF-36 score: Physical Component Summary (PCS) and Mental Component Summary (MCS) scores using non-parametric Wilcoxon-test; if one is statistically significant then the individual domain scores will also be analyzed. Also clinically meaningful improvements \geq Minimum Clinically Important Differences (MCID) of 2.5 points for summary and 5.0 points for domain scores will be analyzed
- Quality of life using FACIT fatigue score will be analyzed using a t-test
- Changes in the levels of auto-antibodies (anti-dsDNA, anti-Smith antigen [anti-Sm], anti-RNP, anti-SSA/Ro, anti-SSB/La, anti-cardiolipin, and anti- β 2-glycoprotein I antibodies) will be analyzed using a t-test
- Changes in the levels of biomarkers (C3, C4, CH50) will be analyzed versus baseline
- Anti-IFN α and anti-KLH antibody isotyping
- Anti-Hemagglutinin antibody response: seroconversion (four fold increase in antibody titers post-vaccination) and seroprotection (HIA antibody titers \geq 1:40 post-vaccination)
- Correlation between immunogenicity responses and clinical or biological parameters will be performed on an exploratory basis

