4.2.1 Adverse events

Adverse events (AE) will be coded using the MedDRA Version 18 and will be classified by Preferred Term (PT) and System Organ Class (SOC).

A Treatment Emergent Adverse Events (TEAE) will be defined as any adverse event that occurs from the time of first study treatment dose administered to the patient until last study visit.

An SAE is defined as an AE that meets one of the following conditions:

- Death.
- Life threatening event (defined as any AE that places the patient, in the view of the Investigator, at immediate risk of death from the event as it occurred, i.e., it does not include an event that had occurred in a more severe form, might have caused death).
- An event requiring inpatient hospitalization or prolongation of existing hospitalization during the period of protocol defined surveillance.
- Results in a persistent or significant disability/incapacity.
- Congenital anomaly or birth defect in the offspring of a study participant.
- Any other important medical event that may not result in death, be life threatening, or require hospitalization, may be considered a serious adverse experience when, based upon appropriate

Statistical Analysis Plan

Study Name: IFN-K-002

SAP version & date: v4, 18/Jun/2018

medical judgment, the event may jeopardize the patient and may require medical or surgical intervention to prevent one of the outcomes listed above. Examples of such medical events include allergic bronchospasm requiring intensive treatment in an emergency room or at home, blood dyscrasias or convulsions that do not result in inpatient hospitalization, or the development of drug dependency or drug abuse.

Tolerability/safety will be assessed over the 36 weeks study period. The analysis will focus on:

- Occurrence and intensity of any solicited local and systemic reactions during a 7-day follow-up period (i.e. day of study product administration and 6 subsequent days) after each IFN-K or placebo dose
- Occurrence, intensity and relationship of unsolicited AEs occurring throughout the study period
- Occurrence, intensity and relationship of all SAEs occurring throughout the study period
- Rate and severity of viral infections
- Flares (time of occurrence in relation to product administration)

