5.2.4.5 Exploratory analyses

The following analysis will be performed on the FAS population except if otherwise specified.

5.2.4.5.1 **PGA scores**

PGA score at each visit and change from baseline by treatment group will be presented. (Statistical tables 14.2.28.1 to 14.2.28.2)

All PGA data will be listed in Listing 16.2.6.10.

5.2.4.5.2 **SLE flares**

Time to first SLE flare in patients will be analyzed using a cox regression model.

The first model will be adjusted on treatment group.

The second model will be performed only on patients IFN-K treated and will be adjusted on presence/absence of neutralizing antibodies. (Statistical tables 14.2.29.1 to 14.2.29.2)

5.2.4.5.3 **28-Tender and Swollen Joint Counts (SJC)**

28-Tender and Swollen Joint Counts and Joint Pain VAS at each visit and change from baseline will be presented. The changes at Week 36 will be analyzed using a t-test. (Statistical tables 14.2.30.1 to 14.2.32.2).

28-Tender and Swollen joint counts data will be listed in Listing 16.2.6.11, and joint Pain VAS data in Listing 16.2.6.12.

5.2.4.5.4 **Treatment failure**

- Proportion of treatment failure will be analyzed using frequency table methods. Patients will be considered as treatment failure if they receive more than 5 mg prednisone equivalent/day at any time between Week 24 (Visit 9) and Week 36 (Visit 12) or if their CS dose is increased above the Week 24 level is recorded (this criterion will be identified by medical review) (Statistical table 14.2.33)

5.2.4.5.5 **SF-36**

Statistical Analysis Plan

Study Name: IFN-K-002

SAP version & date: v4, 18/Jun/2018

Physical Component Summary (PCS) and Mental Component Summary (MCS) scores at each visit and change from baseline will be presented. The changes at Week 36 will be analyzed using a non-parametric Wilcoxon rank sum test (Statistical tables 14.2.34.1 to 14.2.35.2). If one is statistically significant then the individual domain scores will also be described.

In addition, number of patients with clinically meaningful improvements \geq Minimum Clinically Important Differences (MCID) of 2.5 points for summary and 5.0 points for domain scores between baseline and Week 36 will be presented. (Statistical tables 14.2.36 to 14.2.37)

All SF-36 data will be presented in Listing 16.2.6.13.

5.2.4.5.6 **FACIT**

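### Time to first SLE flare: the SAP replaces the protocol's life-table analysis with a Cox model, does not list the change in section 7, and plans no flare proportions over time or proportional-hazards check

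*SAP*

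**What the plan says.** Protocol 13.9.6: "Time to first SLE flare in patients will be analyzed using life-table methods".

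SAP 5.2.4.5.2: "Time to first SLE flare in patients will be analyzed using a cox regression model". Two models follow. For the comparison between arms, "The first model will be adjusted on treatment group". The other is not a treatment comparison: "The second model will be performed only on patients IFN-K treated and will be adjusted on presence/absence of neutralizing antibodies".

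The outputs match that text. SAP 10.1 lists two time-to-flare tables, 14.2.29.1 and 14.2.29.2, one per Cox model. SAP 10.2 lists four figures: one titled "Sensitivity efficacy analysis - First co-primary endpoint - MMRM - Model diagnostic" and three reverse cumulative antibody curves.

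SAP section 7 sets out the departures from the protocol's statistical sections. Its entry for secondary and exploratory analyses (7.2.2) records the added composite SRI-4 and the dropped analysis of changes in lupus therapy. Nothing in section 7 mentions time to flare.

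SAP section 9 defines a flare from BILAG-2004 scoring and dates it at the visit where it is scored. Patients without a flare are censored at Week 36 or at end of study. SAP 4.2.1 names the timing of flares relative to dosing as a safety focus.

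**The concern.** A life table reports the proportion of patients who have flared by each visit, in each arm. A Cox model with treatment as its only term reports one ratio, assumed constant from Week 0 to Week 36. The two answer different questions, and the SAP drops the first without listing that it has done so.

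The constant-ratio assumption is doubtful here. The product has to raise antibodies before it can act. In the earlier study, Protocol 5.4.3 says of signature neutralisation that "it peaks at 8 weeks post-dose 3". Dose 3 is at Week 4, so the peak falls at about Week 12, one third of the way through follow-up. If the clinical effect follows the same course, one ratio describes neither the early nor the later period, and no planned output would show that this had happened. What is at stake is the reading of an exploratory endpoint. No sample size, error rate or success criterion depends on it.

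**Working it through.** **1. Is the change listed?** The introduction to Protocol section 13 says that major deviations and alternative analyses will be described in the SAP. The SAP does describe the Cox model, in 5.2.4.5.2. Section 7, where a reader would look for departures, omits it. The version 2 and 3 entries of the SAP's revision history do not mention it either. The version 4 entry was not in the text available to this review.

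**2. Does another output give flare risk over time by arm?**

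| Output | What it gives | What it lacks |
|---|---|---|
| Tables 14.2.29.1-2 | Cox results | By title, no proportions by visit |
| Table 14.2.13 | SELENA-SLEDAI flares | After baseline, this index is scheduled only at Weeks 24 and 36 |
| Tables 14.2.11-12 | BILAG shift table and global score | No first-flare times |
| Tables 14.3.7.1-6 | Treatment-emergent AEs by arm and dose period | AE-reported flares, unequal intervals, no censoring |

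The dose periods start at Weeks 0, 1, 4, 12 and 24 and end at Week 36, so they last 1, 3, 8, 12 and 12 weeks. BILAG is scored at nine post-baseline visits (Week 4, then every 4 weeks to Week 36). The finer data exist but are not tabulated as flare risk.

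**3. How far can one hazard ratio mislead?** The plan states no flare rate, hazard ratio or power for this endpoint, so there is no figure of its own to reproduce.

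From the protocol: 89 patients per arm, 10% dropout, BILAG visits every 4 weeks, window of 4 days either side. Assumed: placebo flare risk by Week 36, F, of 35% or 50%; constant placebo hazard; hazard ratio r1 to Week 12 and r2 afterwards.

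Cumulative flare risk:
- placebo at week w: 1 − (1 − F)^(w/36)
- IFN-K at Week 12: 1 − (1 − F)^(12·r1/36)
- IFN-K at Week 36: 1 − (1 − F)^((12·r1 + 24·r2)/36)

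*Delayed effect, r1 = 1.0, r2 = 0.5.* The exponent at Week 36 is (12 + 12)/36 = 2/3.
- F = 50%: Week 12, 20.6% in both arms; Week 36, 50.0% placebo and 1 − 0.5^(2/3) = 37.0% IFN-K.
- F = 35%: Week 12, 13.4% in both arms; Week 36, 35.0% and 1 − 0.65^(2/3) = 25.0%.
- Simulated Cox hazard ratio (1,500 trials each, Efron ties): mean 0.71 and 0.69. The direction is right, but the value fits neither 1.0 nor 0.5.

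*Crossing hazards, r1 = 1.8, r2 = 0.6.*
- F = 50%: Week 12, 20.6% placebo and 34.0% IFN-K. F = 35%: 13.4% and 22.8%. Week 36: equal in both cases.
- Simulated Cox hazard ratio: mean 1.11 and 1.07, with p < 0.05 in 8.1% and 5.7% of trials.

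The crossing values were chosen to cancel: 12 × 1.8 + 24 × 0.6 = 36, the placebo total. Fixing r1 = 1.6 and r2 = 0.7 with F = 50% and moving the change point shows the sensitivity (400 trials each):

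| Change at | Mean Cox hazard ratio | p < 0.05 |
|---|---|---|
| Week 8 | 0.97 | 4.0% |
| Week 12 | 1.10 | 6.0% |
| Week 16 | 1.21 | 13.0% |

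With the change at Week 12 this pair also cancels (12 × 1.6 + 24 × 0.7 = 36). The results show that cancelling can occur, not that it is likely.

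**The case against.** The endpoint is exploratory, the Cox model is stated openly, and flare timing is not wholly absent. Protocol 12.1.1 has flares reported as AEs, and SAP 5.2.5.2 tabulates treatment-emergent AEs by arm in periods cut at each dose. The first three periods cover Weeks 0 to 12. Protocol 5.6 also has the iDSMB monitor flares throughout the study. All of this stands and lowers the weight of the point. It does not supply BILAG-defined cumulative flare risk with censoring, which is what the protocol's method would give.

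A reader might go further and infer that the hazard ratio will hide flares provoked early by immunisation. The documents do not support that. Among 21 patients given IFN-K in the earlier study, the Protocol reports that "one flare of underlying lupus occurred for a patient who had received only one injection of IFN-K". That is a single case in a disease the protocol describes as alternating between flare and remission. The timing of neutralisation supports a delayed benefit, not early harm, and no flare rates are given from which crossing hazards could be argued.

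A reader might also infer that the change was concealed. The supportable defect is narrower: it is missing from section 7.

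**Conclusion.** The point holds at low severity. Protocol 13.9.6 and SAP 5.2.4.5.2 specify different analyses, section 7 does not record the difference, and nothing planned shows the cumulative proportion with a BILAG flare by arm or checks proportional hazards.

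Under the assumed delayed effect (hazard ratio 1.0 to Week 12, then 0.5), the reported value would be about 0.69 to 0.71. That would mislead about size and timing but not direction. Cancelling to near 1 needs crossing hazards, for which the documents give no rates and only one isolated case. It should be stated as a possibility and no more. All flare risks and hazard ratios used here are assumptions.

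**What to change.** 1. Declare in SAP 7.2.2 that Cox regression replaces or supplements the life-table method, with the reason.
2. In SAP 5.2.4.5.2, restore life-table or Kaplan-Meier cumulative flare proportions by arm with 95% confidence intervals at each BILAG visit, plus a curve with numbers at risk. Add the table to 10.1 and the figure to 10.2.
3. Keep the Cox model, but state a proportional-hazards check and a method for ties, since flares are dated at visits.
4. Report descriptive hazard ratios for Weeks 0-12 and Weeks 12-36, noting that each is less precise than the overall estimate.

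A log-rank test would not help. It is the score test of the same one-term Cox model, so early and late effects offset in it in the same way.

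The cost is one table, one figure and one extra model term, all from data already derived under SAP section 9. No sample size or error rate changes.
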